Participants who decline PrEP can remain in follow-up (see Section 6.4.1) and can begin PrEP at any time up to and including their Week 39 visit. Enrolling participants who decline PrEP at baseline allows for an assessment of the impact of the intervention on PrEP uptake over time. If a participant has not been provided PrEP on study by Week 39 and decides to initiate PrEP after the Week 39 study visit, PrEP will not be provided at the study site; rather the participant will be linked to local PrEP services (see Section 5.2 for details). Week 39 is the last visit before the end of the first year of the study which will provide information on PrEP uptake. The second year will provide information on PrEP persistence so PrEP cannot be initiated at the site but as noted, participants can be referred.

The multi-component interventional package including GAHT and PHN using SBCM is outlined in Table 3. During the first six months, the Deferred Intervention Arm includes standard HIV prevention interventions such as risk-reduction counseling (Project RESPECT; Prevention Cohort) and provision of PrEP. Participants in the Deferred Intervention Arm will be linked with institutions that have established a partner agreement with the site. A partner agreement at each site will include at a minimum an agreement to provide care to study participants in a timely manner.

Shown in Table 3 is each intervention component, a brief description, the theoretical foundation, and the staff member(s) responsible for component delivery.

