### 8.3 Sample Size

There is limited data on PrEP uptake and adherence specific to the TGW population, with the published data being highly variable. Moreover, the TGW population is a hard to reach population requiring multiple sampling and recruitment strategies. Given the unique challenges described above, the sample size is determined on the basis of the statistical power to detect a hypothesized difference in proportions between the Immediate vs Deferred Intervention arms, taking logistical and operational constraints regarding recruitment of HIV-uninfected TGW into consideration.

Figure 5 shows the number of individuals needed per study arm to achieve 90%, 85%, and 80% statistical power to detect a pre-determined difference in proportions  $p_1 - p_0$  between the Immediate Intervention Arm vs the Deferred Intervention Arm, under 1:1 randomization, with  $p_1$  and  $p_0$  denoting the proportion of HIV-uninfected TGW satisfying the condition of interest in the Deferred and Immediate Intervention Arms respectively. The horizontal axis depicts a range of plausible values of  $p_1 - p_0$ .

**Figure 5.** Sample sizes needed to achieve power (80%, 85%, 90%) for a two-sided test in proportions for an individually randomized trial with 1:1 randomization based on different values of hypothesized differences in proportions. For PrEP adherence, the hypothesized value under the alternative is 0.2.

Current research on PrEP uptake is limited, although existing data show low rates of PrEP uptake among TGW. Among HIV-uninfected TGW randomized to the Immediate Intervention vs. Deferred Intervention Arms, the study is being powered to detect a 20 percentage-point difference in PrEP adherence and a 25 percentage-point difference in PrEP uptake between the Deferred Intervention Arm and Immediate Intervention Arm at Week 26. We assume that the uptake, adherence and retention rates will be the same for the two PrEP agents (FTC/TAF and FTC/TDF).

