#### 8.4 Accrual and Retention

Approximately 310 HIV-uninfected TGW will be enrolled and randomized to the Immediate and Deferred Intervention Arms across the five study sites. An average annual retention rate of at least 85 percent will be targeted. Differential enrollment targets will be considered for the sites, with higher enrollment targeted for the Brazil site and competitive enrollment among remaining U.S sites. We estimate 560 TGW will be screened for the study to achieve the enrollment target of approximately 310 TGW (80% of TGW screened).

a Considering that the variance, and therefore sample size is largest when  $p=0.5$ , we obtain conservative sample sizes by setting  $H_0: 0.5 - d/2$  and  $H_1: 0.5 + d/2$ , where  $d$  is the hypothesized difference in proportions between intervention and Deferred intervention arms.

b Note that since the hypothesized effect size for PrEP adherence is smaller than for PrEP uptake (20% vs 25%), the sample size needed to achieve 90% power based on PrEP adherence will also achieve greater power for PrEP uptake, hence powering the sample size for the prevention cohort study on PrEP adherence.

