## **8.5 Random Assignment/Study Arm Assignment**

A stratified/block randomized trial will be used, stratifying differentially by site. Differential number of TGW will be enrolled at each site and randomized 1:1 using a random number generator to each study arm.

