## **8.6 Statistical Analysis**

This section briefly describes the final study analyses. Detailed technical specifications of the statistical analyses will be described in a separate Statistical Analysis Plan.

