The proportion of individuals on each of the two PrEP agents (Truvada® vs Descovy®) will be reported at baseline, 13- and 26-week visits. If a significant imbalance is detected between arms at any of these visits, the primary analysis will be adjusted for PrEP agent using regression and/or causal inference methods. Similar strategies will also be employed if differential missingness is observed in each of the primary endpoints between the two arms.

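### The imbalance-triggered adjustment for PrEP agent in Section 8.6.1 can strip the uptake-driven part out of the primary adherence effect

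*Combined protocol and SAP*

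**What the plan says.** Section 8.6.1 defines both Week 26 primary proportions, uptake and adherence, over all enrolled participants. Adherence means confirmed protective drug levels. The section then reports the proportion on each of the two agents at baseline, Week 13 and Week 26, and adds that if a significant imbalance in agent is "detected between arms at any of these visits, the primary analysis will be adjusted for PrEP agent using regression and/or causal inference methods". It gives no test, no denominator for the imbalance, no coding for participants on no agent, no estimand, and no indication of which visit's agent enters the model.

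Other sections bear on this:

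- Section 6.3 makes randomisation the point of enrolment. Section 5.2 lets participants enrol without accepting PrEP, start it later and switch agents. Section 3.1 explains why decliners are included: "Enrolling participants who decline PrEP at baseline allows for an assessment of the impact of the intervention on PrEP uptake over time".
- Section 8.3 states that "the study is being powered to detect a 20 percentage-point difference in PrEP adherence and a 25 percentage-point difference in PrEP uptake" at Week 26, and also: "We assume that the uptake, adherence and retention rates will be the same for the two PrEP agents".
- The sample-size footnote, printed under Section 8.4, says "we obtain conservative sample sizes by setting" the two proportions at 0.5 - d/2 and 0.5 + d/2.
- Brazil offers Truvada only (Sections 5.1 and 5.2). Section 8.4 plans differential site targets, "with higher enrollment targeted for the Brazil site and competitive enrollment among remaining U.S sites". Section 8.5 adds: "A stratified/block randomized trial will be used, stratifying differentially by site".
- Section 8.6 defers detail: "Detailed technical specifications of the statistical analyses will be described in a separate Statistical Analysis Plan".

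**The concern.** Agent in use at Week 13 or 26 is a consequence of what happened after assignment in an open-label trial. Even the baseline value is doubtful, because the U.S. agent choice and randomisation fall at the same visit and their order is not stated.

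Agent also carries uptake information, since a participant has an agent only if she has taken up PrEP. For the uptake endpoint, adjusting for agent amounts to adjusting for the outcome. For adherence, uptake lies on the path from intervention to outcome. A regression that conditions on agent then compares arms within levels of PrEP use and discards whatever the intervention achieved by getting more people onto PrEP.

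At stake is the meaning of the primary contrast. If the rule fires and is met by plain regression, the result no longer estimates the as-randomised difference among all enrolled. If imbalance is judged over all enrolled, a successful uptake effect is itself an agent imbalance, so the better the intervention works on uptake, the likelier its effect is adjusted away.

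**Working it through.** **1. The plan's own figure.** With d = 0.20 the footnote gives 0.40 versus 0.60. At two-sided 5% and 90% power, n per arm = (1.960 + 1.282)² × 2 × 0.25 / 0.20² = 131.3, against 131 stated. Then 262/0.85 = 308, against about 310. The 40%/60% alternative is therefore the one the plan uses.

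**2. Inputs.** Let u0 and u1 = u0 + 0.25 be uptake in the Deferred and Immediate Arms. Adherence among PrEP users is then 0.40/u0 and 0.60/u1. The plan does not give u0. It must be at least 0.40, because adherent participants must be users (assuming protective levels occur only in those who started PrEP). It can be at most 0.75, because u1 cannot exceed 1. Assumed: user adherence within an arm does not differ by agent, and the agent mix among users is the same in both arms.

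**3. Formula.** The least-squares arm coefficient, adjusted for a categorical covariate, is the average of the within-category arm differences with weights n1·n0/(n1 + n0).

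**4. No agent coded as its own category.** The difference among participants on no agent is zero. Among users it is D = 0.60/u1 - 0.40/u0. The weights are W_users = u0·u1/(u0 + u1) and W_none = (1 - u0)(1 - u1)/[(1 - u0) + (1 - u1)]. The coefficient is D × W_users/(W_users + W_none), and the Descovy share cancels.

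| u0 / u1 | D | W_users | W_none | Adjusted effect (points) |
|---|---|---|---|---|
| 0.40 / 0.65 | -0.0769 | 0.2476 | 0.2211 | -4.1 |
| 0.50 / 0.75 | 0 | 0.3000 | 0.1667 | 0.0 |
| 0.60 / 0.85 | 0.0392 | 0.3517 | 0.1091 | 3.0 |
| 0.70 / 0.95 | 0.0602 | 0.4030 | 0.0429 | 5.4 |
| 0.75 / 1.00 | 0.0667 | 0.4286 | 0 | 6.7 |

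The unadjusted difference is 20 points in every row. Dropping decliners because their agent is missing also gives 0.0 at 50% versus 75%, since D is zero there.

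**5. Descovy yes/no over all enrolled.** Take uptake 50% versus 75% and a Descovy share of users of 52.5% (30% of enrolment in Brazil, 75% of U.S. users on Descovy: 0.70 × 0.75).

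- Not on Descovy, Deferred: 0.19/0.7375 = 0.2576. Immediate: 0.285/0.60625 = 0.4701. Difference 0.2125, weight 0.3327.
- On Descovy: difference 0, weight 0.1575.
- Coefficient: 0.2125 × 0.3327/0.4902 = 14.4 points.

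Shares of 30% and 67.5% give 17.4 and 11.6. Over all permitted uptake levels and these shares the range is 8.4 to 19.4.

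**6. Smaller uptake differences.** At 65% versus 75%, with adherence still 40% versus 60%, the results are 13.0 points (no agent as a category) or 18.3 (yes/no, share 52.5%). Equal uptake with an equal agent mix loses nothing.

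**7. How often the rule fires.** A two-proportion test at 5% is assumed, since none is stated.

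- *Over all enrolled, ignoring site.* With 155 per arm, a 60% share and uptake 50% versus 75%, 30% versus 45% are on Descovy. The standard error is 0.0550 under the null and 0.0543 under the alternative, so z = (0.15 - 1.96 × 0.0550)/0.0543 = 0.78. That is about 78% at one visit (simulated: 79%).
- *Central case by simulation.* Assumed: Brazil 30%, 75% of U.S. users on Descovy, 20% re-choosing between visits, uptake 50% versus 75%, and the Brazil share fixed in each arm by stratification. Over all enrolled the rule fires in about 73% of trials at one visit. Varying Brazil share, U.S. choice, re-choosing and u0 gives 30% to 92%.
- *Among users, with no true imbalance.* About 2% per visit and 4-5% over three visits (ranges 0.2-4.1% and 0.2-10.4%). Ignoring site it is about 5% per visit and at most 1 - 0.95³ = 14.3% over three.

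**8. Rejection rate of the whole procedure** (central case, 155 per arm, adjusted result used only when the rule fires):

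| Procedure | Rejects |
|---|---|
| Unadjusted | 94% |
| User-mix trigger, no agent as a category, one visit / three visits | 92% / 90% |
| All-enrolled trigger, one visit, Descovy yes/no | 84% |
| All-enrolled trigger, one visit, no agent as a category | 27% |

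**The case against.** The strongest reply is that the text names a two-agent contrast, so the natural reading is the mix among PrEP users. On that reading the rule rarely fires by chance and rejection drops only from 94% to 90-92%. This is a fair reading, but the text does not establish it. The 27% figure does need three things at once: an all-enrolled trigger, plain regression and a no-agent category.

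Second, the 20-point and 25-point differences are separate power targets, and 40%/60% is a variance-maximising device. Applied to uptake, the same device gives 37.5% versus 62.5%, which cannot coexist with 40% adherent in the Deferred Arm. Eligibility also requires interest in PrEP, so uptake may be high and similar in both arms. At 80% versus 90%, with adherence still 40% versus 60%, 14.4 points (no agent as a category) or 19.2 (yes/no) remain. This stands as a limit on the size: the 6.7-point ceiling belongs to the two targets taken together.

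Third, that ceiling also assumes equal adherence by agent. Suppose uptake of 75% versus 100%, Descovy shares of 70% versus 30%, and Descovy users 20 points more adherent in each arm. Truvada users are then 39.3% versus 54.0% adherent and Descovy users 59.3% versus 74.0%, so 14.7 points remain. That is correct arithmetic, but it departs from the equality assumed in Section 8.3.

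Fourth, the rule has a purpose, because protective thresholds may differ by agent. A causal method with a clear estimand could serve that purpose, and the separate SAP could specify one. But the rule does not require a causal method. A SAP that dropped the adjustment would contradict the protocol's commitment that the primary analysis will be adjusted.

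**Conclusion.** The concern holds. As written, the rule allows the primary adherence comparison to be replaced by one conditioned on a post-randomisation variable that is undefined for decliners and that encodes uptake. This goes beyond missing detail, because a permitted way of following the rule gives a different and attenuated estimand.

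That conclusion rests on the text alone and is firm. The size depends on further assumptions: the plan's two targets taken jointly, and adherence within arm unrelated to agent. On those, 20 points become -4.1 to +6.7 with a no-agent category, or 8.4 to 19.4 with Descovy yes/no. The less of the effect that runs through uptake, the smaller the loss. The trigger rates rest on assumed site shares, agent choices and a 5% test, and they turn chiefly on a denominator the plan leaves open. The point should be fixed, although the harm arises only if the rule fires and is met by plain regression.

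**What to change.** Delete the imbalance-triggered adjustment for agent from the primary analysis in Section 8.6.1. In every case, keep the as-randomised Week 26 comparisons of uptake and adherence among all enrolled participants as primary, not adjusted for agent. Report agent by arm descriptively at baseline, Week 13 and Week 26, with the denominator stated. Address agent differences, including agent-specific thresholds, in one pre-specified sensitivity analysis of adherence that states its estimand, method and handling of participants on no agent.

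The cost is protocol and SAP wording plus one small analysis. Sample size, visits and data collection do not change.

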## 8.6.2 Secondary Analyses

The data analysis plan is described below for each secondary endpoint defined in Section 8.2.2.

### Incident HIV-infections

Descriptive statistics will be obtained for the number of incident HIV infections at each time point by arm. Poisson regression models with person time will be used for estimating HIV incidence by arm.

### Sexually transmitted infections (STIs)

Descriptive summaries will be used to present the number of active bacterial STIs and the HBV infections at baseline as compared to selected subsequent visits for each study arm. Logistic regression models will be used to calculate STI prevalence at each time point and Poisson regression models will be used to calculate STI incidence by arm.

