### Integrating HIV Prevention, Gender-Affirmative Medical Care, and Peer Health Navigation for Transgender Women in the Americas: A Vanguard Study

#### SCHHEMA

Purpose:	To assess the feasibility, acceptability, and preliminary impact of a multi-component strategy to improve pre-exposure prophylaxis (PrEP) uptake and adherence that integrates delivery of biomedical HIV prevention co-located with gender-affirming transgender care (hormonal therapy and medical monitoring) and Peer Health Navigation (PHN) using Strengths-Based Case Management (SBCM) professional supervision.
Design:	Multi-site, open-label study with each participant randomized 1:1 to Immediate Intervention vs. 6-month Deferred Intervention Arms. Both arms will be provided PrEP and sexually transmitted infection (STI) screening and treatment. Participants in the Immediate Intervention Arm will receive co-located gender-affirming medical care and PHN using SBCM starting at the Enrollment Visit. Participants in the Deferred Intervention Arm will receive linkage to external gender-affirming medical care and case management services during the deferred period and will transition to the study intervention six months following the Enrollment Visit.
Population:	Transgender Women (TGW), ages 18 or older, HIV-uninfected, at risk of acquiring HIV infection.
Study Size:	Approximately 310 HIV-uninfected TGW.
Study Duration:	For each individual site, the duration of the study is approximately 36 months from the time of site activation. Accrual will require approximately 15 months (3 months for Implementation testing and 12 months for general study); individual participants will be followed for 18 months. Once enrolled, each participant will complete eight follow-up visits.
Study Sites:	Study sites will be listed in the Study Specific Procedures (SSP) Manual and will include four sites in the United States (U.S.) and one site in Brazil.
Study Regimen:	The Intervention will include an approved PrEP agent (Descovy® and Truvada® in the U.S., Truvada® in Brazil), STI screening and treatment, co-located gender-affirming medical care, and PHN using SBCM.

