### **2.2 Secondary Objectives**

The secondary objectives of this study are:

- To determine annual incidence of HIV infection among study participants.
- To determine baseline prevalence and annual incidence of STIs (*Neisseria gonorrhoeae* [GC], *Chlamydia trachomatis* [CT], and *Treponema pallidum* (syphilis)) and to examine changes in STI incidence over time by study arm.

- To examine changes in sexual risk-taking behavior (e.g., number of serodiscordant or HIV-unknown serostatus sexual partners; number of condomless anal/vaginal sex episodes with these partners).
- To obtain baseline laboratory data to evaluate the cohort's suitability for future PrEP intervention studies (e.g., prevalence of renal insufficiency, hepatitis B virus (HBV) infection, hepatitis C virus (HCV) infection, etc.).
- To identify demographic, behavioral, socioeconomic, and psychosocial factors related to: (1) PrEP uptake and PrEP adherence over time, (2) PrEP persistence, and (3) interest in future HIV research, including research involving injectable and implantable agents for PrEP among HIV-uninfected TGW.
- To assess use of medically-prescribed and non-prescription gender-affirming interventions, including exogenous hormones, soft tissue fillers/silicone, and feminizing surgeries (e.g., breast augmentation, vaginoplasty/labiaplasty, orchectomy, etc.).

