## **6.4 Follow-Up Visits**

Follow-up visits will occur on a quarterly basis at Week 13 (Month 3), Week 26 (Month 6), Week 39 (Month 9), Week 52 (Month 12), Week 65 (Month 15), Week 78 (Month 18) after enrollment, as per Appendix Ia. Mental health assessment will be included as part of the medical and physical history assessment. Specific visit windows are outlined in Section 6.5 of the protocol. Per Section 6.3, participants initiating/re-initiating GAHT will need a GAHT initiation visit up to 10 days after collection of samples for review of baseline endogenous estradiol and testosterone concentrations. See Section 6.4.2 for information on re-initiation procedures.

Fasted samples for lipid profile testing will be collected at Week 26 (Month 6) and Week 78 (Month 18). Prior to sample collection, sites must confirm with participants that they have fasted for at least 8 hours, preferably 12 hours, prior to sample collection. If a participant has not fasted, the sample should not be collected for lipid testing, and the participant should be scheduled to return for sample collection ideally within 72 hours from the visit.

Participants who voluntarily withdraw from the study or are lost to follow-up will be contacted for an interview to explore reasons for no longer participating. These interviews can be conducted either in person or by phone, based on participant's availability and/or preference.

Week 78 (Month 18) will serve as the Termination Visit. Prior to this visit, participants should be linked to local providers for PrEP, hormonal therapy, and/or STI testing and treatment, as needed, per site SOP.

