#### **8.2.2 Secondary Endpoints**

Consistent with the secondary study objectives of determining annual incidence of HIV infection, the following endpoint will be assessed:

- Number of documented incident HIV infections during follow-up.

Consistent with the secondary study objectives of determining baseline prevalence and annual incidence of STIs (gonorrhea [GC], chlamydia [CT], and syphilis) and to examine changes in STI incidence over time by study arm, the following endpoint(s) will be assessed:

- Prevalence of STI infection (GC, CT, syphilis) at baseline.
- Incidence of STI infection (GC, CT, syphilis) during follow-up.

Consistent with the secondary study objective of examining changes in sexual risk-taking behavior (e.g., number of serodiscordant or HIV-unknown serostatus sexual partners; number of condomless anal/vaginal sex episodes with these partners):

- Sexual risk-taking behaviors (e.g., number of serodiscordant or HIV-unknown serostatus sexual partners; number of condomless anal/vaginal sex episodes with these partners) measured by ACASI assessments at enrollment and quarterly through Week 78.

Consistent with the secondary study objective of evaluating the cohort's suitability for future PrEP intervention studies (e.g., prevalence of renal insufficiency, hepatitis B virus (HBV) infection, hepatitis C virus (HCV) infection, etc.), the following endpoint(s) will be assessed:

- Baseline laboratory data on all participants.

Consistent with the secondary study objective to identify demographic, behavioral, socioeconomic, and psychosocial factors related to: (1) PrEP uptake and PrEP adherence over time, (2) PrEP persistence, and (3) interest in future HIV research, including research involving injectable and implantable agents for PrEP among HIV-uninfected TGW:

- Individual-level qualitative interview data on a subset of participants addressing core reasons for initiating, discontinuing and/or refusing PrEP.
- ACASI data addressing core reasons for initiating, discontinuing and/or refusing PrEP.
- Interest in future HIV research, collected at Enrollment and Weeks 26, 52, and 78.
- Additional demographic, behavioral, socioeconomic, and psychosocial characteristics collected at Enrollment and quarterly through Week 78.

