### **10.1 Local Laboratory Specimens**

As listed in Appendix Ia and Ib, the following types of specimens will be collected for testing at the local laboratory (LL):

- HIV testing (see SSP Manual)
- HBV and HCV testing to include HBsAg, HBsAb, HBcAb-total, HCV antibody tests
- CBC (complete blood count) with differential
- Creatinine for creatinine clearance.
- Chemistry testing (blood-urea nitrogen (BUN) or urea, albumin, and potassium)
- LFTs (AST, ALT, TBili, alkaline phosphatase)
- Fasting lipid profile (total cholesterol, high-density lipoprotein (HDL), triglycerides, low-density lipoprotein (LDL) – calculated or measured; participants should fast for at least 8 hours, preferably 12 hours, prior to sample collection for lipid testing).
- Estradiol and total testosterone
- Syphilis serologic testing
- Dipstick urinalysis (protein and glucose)
- Rectal swabs, pharyngeal swabs, and urine for GC/CT nucleic acid amplification testing (NAAT)

- CD4 cell count (if HIV-infected)
- Real-time resistance testing for clinical management, if indicated and available (if HIV- infected)

Local laboratories will perform Chemistry and Hematology tests as indicated in Appendix I.

If the HIV testing algorithm includes HIV rapid testing, that testing may be performed in the clinic or laboratory.

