## Appendix Ia: Schedule of Events

	SCR	ENR	GAHT Initiation Visit 	Week 13 (Month 3)	Week 26 (Month 6)	Week 39 (Month 9)	Week 52 (Month 12)	Week 65 (Month 15)	Week 78 (Month 18)
Administrative and Behavioral Procedures									
Informed Consent	X	X							
Demographic information	X								
Locator information	X	X	X	X	X	X	X	X	X
Randomization		X							
ACASI 		X		X	X	X	X	X	X
HIV prevention counseling (offer condoms/lube)	X	X		X	X	X	X	X	X
Provision of PrEP 		X		X	X	X	X	X	
PrEP counseling and support 		X		X	X	X	X	X	X
Provision of GAHT 			X	X	X	X	X	X	
GAHT counseling and support 			X	X	X	X	X	X	X
Peer Health Navigation using Strengths-Based Case Management 		X		X	X	X	X	X	X
Clinical Procedures									
Complete medical history, physical	X								
Symptom-directed physical exam	X	X		X	X	X	X	X	X
Interim medical history (including STI symptoms)		X		X	X	X	X	X	X
Concomitant medications	X	X		X	X	X	X	X	X
Blood collection	X	X		X	X	X	X	X	X
Urine collection for urinalysis	X								

	SCR	ENR	GAHT Initiation Visit 	Week 13 (Month 3)	Week 26 (Month 6)	Week 39 (Month 9)	Week 52 (Month 12)	Week 65 (Month 15)	Week 78 (Month 18)
Urine collection for GC/CT testing		X		X	X	X	X	X	X
Swab (rectal and pharyngeal) collection for GC/CT testing		X		X	X	X	X	X	X
STI treatment, if indicated	X	X		X	X	X	X	X	X
Hepatitis B vaccination or decline of vaccination		X							
Laboratory Procedures									
Dipstick urinalysis (protein and glucose)	X								
GC/CT for NAAT (rectal, urine, pharyngeal)		X		X	X	X	X	X	X
CBC w/differential		X			X		X		X
LFTs (AST, ALT, TBili, alkaline phosphatase)	X			X	X	X	X	X	X
Fasting lipid profile 	X				X				X
Chemistry testing (BUN or urea, albumin and potassium)	X			X	X	X	X	X	X
Creatinine clearance	X			X	X	X	X	X	X
Estradiol and total testosterone testing		X		X	X	X	X	X	X
Syphilis testing		X		X	X	X	X	X	X
HIV testing	X	X		X	X	X	X	X	X
HBV testing (HBsAg, HBsAb, HBcAb-Total)	X								X

	SCR	ENR	GAHT Initiation Visit 	Week 13 (Month 3)	Week 26 (Month 6)	Week 39 (Month 9)	Week 52 (Month 12)	Week 65 (Month 15)	Week 78 (Month 18)
HCV testing	X								X
Plasma storage	X	X		X	X	X	X	X	X
Serum storage		X	X 	X	X	X	X	X	X
DBS storage		X		X	X	X	X	X	X

Mental health assessment will be included as part of the medical and physical history assessment.

If participant accepts PrEP.

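### STI incidence is to be modelled by Poisson regression with no stated allowance for within-person correlation or overdispersion, so its intervals would be too narrow if every infection is counted, standard errors are model-based and infection rates differ between participants

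*Combined protocol and SAP*

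**What the plan says.** The secondary objective in Section 2.2 is, in part, "to examine changes in STI incidence over time by study arm". The matching endpoint in Section 8.2.2 is "Incidence of STI infection (GC, CT, syphilis) during follow-up". The analysis in Section 8.6.2 is one clause: "Poisson regression models will be used to calculate STI incidence by arm".

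On data collection, Section 6.4 says "Follow-up visits will occur on a quarterly basis", and Appendix Ia shows testing for all three organisms at each of the six visits from Week 13 to Week 78. The same schedule lists "STI treatment, if indicated" at each of them. The Schema says "individual participants will be followed for 18 months".

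The neighbouring paragraph on HIV is slightly fuller: "Poisson regression models with person time will be used for estimating HIV incidence by arm". The STI clause does not mention person time. Nothing says whether first or all infections count, whether organisms are pooled, or how repeated observations on one person are handled. Section 8.6.3 names a longitudinal model, but only for perceived drug-hormone interactions.

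**The concern.** Ordinary Poisson regression takes the variance of a count to equal its mean. When some participants have persistently higher infection rates than others, person-level counts vary more than that, and model-based standard errors are too small.

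Unequal rates are likely here. Section 4.1 admits a participant on any one of three different risk criteria, and the sites are in two countries. Quarterly testing with treatment lets reinfection be seen. An objective about change over time also suggests more than one observation per person.

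At stake are the stated precision of the STI rates in each arm and of any comparison between arms. Intervals that are too tight could make a chance difference look like an effect of the intervention on STI incidence.

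**Working it through.** **The plan's own figures.** No STI rate, event count, power or precision is given. The only main-study sample size is for PrEP adherence: 262 evaluable and 310 enrolled. With 0.40 against 0.60, two-sided 0.05 and 90% power, the pooled two-proportion formula gives 130 per arm, or 260. Then 262 / 0.85 = 308.2, rounded up to 309. Both agree with the plan to within 2. Here they matter only as the source of the number of participants.

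**Inputs from the protocol.** 310 participants randomized 1:1, so 155 per arm; six quarterly follow-up visits; three organisms; 1.5 years of follow-up; 85% annual retention (Section 8.4).

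**Assumptions, not in the documents.** Total STI rate of 0.2, 0.5 or 1.0 per person-year. Each person's rate is multiplied by a gamma factor with mean 1 and variance v = 0.5, 1 or 2 (v = 0 means equal rates).

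**Step 1: formula, all infections counted, full follow-up.** With mean count μ = rate × 1.5, the variance is μ(1 + μv), where Poisson assumes μ. The standard error should therefore be larger by √(1 + μv), and the nominal 95% interval covers 2Φ(1.96/√(1 + μv)) − 1. For 0.5 per person-year and v = 2: μ = 0.75, 1 + 0.75 × 2 = 2.5, factor 1.58, coverage 78.5%.

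| Rate per person-year | μ | Factor at v = 0.5 / 1 / 2 | Coverage, % |
|---|---|---|---|
| 0.2 | 0.30 | 1.07 / 1.14 / 1.26 | 93.2 / 91.4 / 87.9 |
| 0.5 | 0.75 | 1.17 / 1.32 / 1.58 | 90.5 / 86.2 / 78.5 |
| 1.0 | 1.50 | 1.32 / 1.58 / 2.00 | 86.2 / 78.5 / 67.3 |

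**Step 2: simulation with dropout and quarterly detection.** 1,000 trials per setting, no true arm effect, rate split 40:40:20 across organisms, Poisson model for the between-arm rate ratio with a person-time offset.

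| Rate per person-year | Robust / model-based SE at v = 0.5 / 1 / 2 | Coverage of plain Poisson interval, % |
|---|---|---|
| 0.2 | 1.05 / 1.10 / 1.20 | 92.8 / 93.8 / 91.1 |
| 0.5 | 1.11 / 1.23 / 1.42 | 92.8 / 89.7 / 82.1 |
| 1.0 | 1.21 / 1.39 / 1.66 | 91.8 / 85.2 / 76.8 |

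Simulation error at 95% coverage is √(0.95 × 0.05 / 1000) = 0.7 points, which accounts for the uneven first row. In the same nine settings, person-level robust errors covered 93.9% to 96.2%, and plain Poisson for the first infection of any kind covered 94.2% to 96.6%. With v = 0 and all infections counted, plain Poisson covered 94.5% to 96.1%. The factors are smaller than in Step 1 because dropout shortens follow-up and each organism is detected at most once per quarter.

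**Step 3: a shorter contrast.** Under Section 3.1 the arms receive different services only in the first 6 months. At 0.5 per person-year, μ = 0.5 × 0.5 = 0.25, and the formula gives √(1 + 0.25 × 0.5) = 1.06 to √(1 + 0.25 × 2) = 1.22, against 1.17 to 1.58 over 18 months.

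**Step 4: scope.** These factors apply to arm-specific rates and between-arm ratios. They do not carry over to a change from early to late follow-up within the same people: a stable personal rate multiplies both counts and largely cancels from their ratio. Participant-clustered variance is suitable for both kinds of contrast.

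**The case against.** The protocol does not say that standard errors are model-based, nor that every infection counts. Poisson regression with a robust variance would still fit its wording. One first-infection analysis per participant would also fit, and in the check that has no under-coverage. Section 8.6 calls itself brief and leaves technical specifications to a separate SAP, which is not in the text available here and may already settle this. The sizes rest on assumed rates and variances and are small at low incidence. The clause describes estimation: no test or alpha is stated for STIs.

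All of that stands, and it makes the point conditional. It does not remove it. An endpoint covering three treatable infections throughout follow-up, with an objective about change over time, reads most naturally as several observations per person. A first-infection count fits that objective poorly, because it progressively removes the highest-risk participants from later periods.

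A reader might infer that repeat infections, or three organisms, by themselves invalidate Poisson regression. They do not: with equal rates across people, coverage was correct with both present. The cause is within-person correlation or overdispersion.

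**Conclusion.** The point holds conditionally. The stated method makes no allowance for within-person correlation or overdispersion, in a design that will probably produce both. If all infections are counted with model-based variance and rates differ between people, correct intervals for by-arm incidence are about 1.05 to 1.66 times as wide as the plain Poisson ones, and nominal 95% coverage falls to between about 94% and 77%. This assumes 0.2 to 1.0 infections per person-year and between-person variance of 0.5 to 2. At the low end the effect is minor.

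A reader might go further and infer that the reported intervals will certainly be wrong, or that the trial carries a known false-positive rate for STIs. The documents support neither: the counting rule and variance method are unstated, the SAP detail is deferred, and no STI test is specified. The analysis is secondary; the primary comparison and the sample size are unaffected.

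**What to change.** In the STI paragraph of Section 8.6.2 and in the SAP, state:

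- Poisson regression with a person-time offset and participant-clustered robust variance (sandwich or GEE), or a negative binomial model, for STI incidence and for its by-arm and over-time contrasts;
- whether all infections or only the first are counted, with the time at risk that follows from that choice;
- whether organisms are analysed separately or as a composite.

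If the SAP already says this, only the protocol paragraph needs aligning. The change is a few lines of text and needs no new data. With robust variance the rate and rate ratio keep their meaning, and the intervals remain valid whether or not overdispersion is present. The cost is somewhat wider intervals when it is.
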